**CONFIDENTIAL INFORMATION**

MD133254 Statistical Analysis Plan Template

Revision#: 1

Doc Type: GC

The hypothesis will be tested using a two-sample binomial proportions test:

$$z = \frac{p_C - p_T}{\sqrt{\frac{p_C(1-p_C)}{n_C} + \frac{p_T(1-p_T)}{n_T}}}$$

where:

$p_C$  = observed brain infarct proportion in control group

$n_C$  = number of evaluable subjects in control group

$p_T$  = observed brain infarct proportion in test group

$n_T$  = number of evaluable subjects in test group

The test statistic  $z$  is assumed to have a standard Normal distribution. The significance level for this test will be set at a 1-sided  $\alpha = 0.025$ , but the p-value will be adjusted for multiplicity with the 1-sided  $\alpha = 0.025$  test performed simultaneously on the primary endpoint. Therefore,  $p_C - p_T > 0$  and a multiplicity-adjusted p-value  $\leq 0.025$  will result in rejection of the null hypothesis in favor of the alternative hypothesis and a conclusion that the test treatment reduces the rate of brain infarct compared to the control treatment. The 1-sided multiplicity-adjusted p-value and unadjusted 2-sided 95% confidence interval for the difference in proportions will be reported.

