The test statistic *z* is assumed to have a standard Normal distribution. The significance level for this test will be set at a 1-sided $\alpha = 0.025$, but the p-value will be adjusted for multiplicity with the 1-sided $\alpha = 0.025$ test performed simultaneously on the primary endpoint. Therefore, $p_C - p_T > 0$ and a multiplicity-adjusted p-value ≤ 0.025 will result in rejection of the null hypothesis in favor of the alternative hypothesis and a conclusion that the test treatment reduces the rate of brain infarct compared to the control treatment. The 1-sided multiplicity-adjusted p-value quad unadjusted 2-sided 95% confidence interval for the difference in proportions will be reported.

[figure not shown]

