2.9. Interim Analyses

The original protocol specified that, in addition to standard study monitoring, an interim analysis will be performed after approximately 50% of the total expected recurrent stroke or imaging-confirmed TIA events have occurred. This milestone event had not occurred as of the completion of full enrollment in February 2015. Under the plan described herein, the original interim analysis plan no longer serves its purpose and is rescinded.

A new interim analysis that does not involve any statistical hypothesis testing is anticipated to occur around April 2016. No analyses that would require alpha spending are planned for this interim analysis.

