3.3. Subject Population

Subjects will be enrolled at a maximum of eighty (80) investigational sites in the United States, Canada and Europe. All potential subjects must have been diagnosed with cryptogenic stroke or imaging-confirmed TIA and the presence of a PFO and be at risk for recurrent stroke or TIA event.

Eligible subjects will be randomized to a treatment arm in a 2:1 fashion (device-to-antiplatelet medical therapy). This randomization will result in approximately 443 in the test (device) arm and 221 subjects in the control (antiplatelet medical therapy) arm.

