### 2.3 Randomization and Enrollment

A patient is considered an enrolled subject in the study upon randomization to one of the two treatment arms, Test or Control. Randomization will be weighted 2:1 in favor of the test arm. The randomization plan does not stratify by site or any other baseline variables.

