## 2.7 Sample Size Determination

### 2.7.1 Sample Size Assumptions

Based on literature available at the study's initiation (see Section 1.0 of the study protocol), the proportion of PFO patients free from a recurrent stroke or imaging-confirmed TIA at 24 months after initial, cryptogenic stroke or imaging-confirmed TIA is assumed to be approximately 92%, with a range of 86% to 94%. For the purposes of determining sample size for adequate power, a 55% reduction in the hazard of a recurrent stroke or imaging-confirmed TIA is considered a clinically relevant benefit.

At the time this study was designed, Co-primary Endpoint 2 was considered a secondary endpoint and was not relevant to the sample size assumptions.

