### 4.2.2 Interim Analyses

The original protocol specified that, in addition to standard study monitoring, an interim analysis will be performed after approximately 50% of the total expected recurrent stroke or imaging-confirmed TIA events have occurred. This milestone event had not occurred as of the completion of full enrollment in February 2015. Under the plan described herein, the original interim analysis plan no longer serves its purpose and is rescinded.

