### 4.3.2 Brain Infarct

The analysis sample for Co-primary Endpoint 2, brain infarct, will consist of randomized subjects with valid MRI Core Lab data at screening and an appropriate follow-up, where follow-up will be at 24 months or immediately following a recurrent event (suspected stroke or TIA), whichever occurs first, as well as randomized subjects who experience a confirmed recurrent event through 24 months regardless of MRI data status. Responders are subjects who show one or more new infarction(s) on MRI since screening or experience a confirmed recurrent event. Nonresponders are subjects who do not show new infarction on MRI since screening and do not experience a confirmed recurrent event.

The primary analysis will be a two-sample comparison of the binomial proportion of subjects with brain infarct between the two treatment groups. Each binomial proportion will be calculated as the count of responders divided by the count of evaluable subjects (sum of the responder and nonresponder counts).

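### Should Boschloo's exact test replace the unpooled z for Co-primary Endpoint 2, since 2:1 allocation makes the z mildly conservative?

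*SAP*

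**What the plan says.** SAP 4.3.2 says of the brain infarct endpoint: "The hypothesis will be tested using a two-sample binomial proportions test". The formula beneath divides the difference in observed proportions by the square root of the two arms' separate binomial variances, so the variance is unpooled. Protocol 2.8 prints the same formula and adds that z "is assumed to have a standard Normal distribution". The level is one-sided 0.025. The p-value is adjusted for multiplicity with Endpoint 1 before it is compared with that level, and an unadjusted two-sided 95% interval for the difference is reported beside it.

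On allocation, SAP 2.3 says "Randomization will be weighted 2:1 in favor of the test arm", and Protocol 3.3 expects "approximately 443 in the test (device) arm and 221 subjects in the control (antiplatelet medical therapy) arm".

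No Endpoint 2 event rate can be read in the public copy. Protocol 2.6.4, the power section for this test, appears only in the table of contents, and the SAP 4.5 text on multiplicity is largely unreadable. The nearest figure is the Endpoint 1 assumption in SAP 2.7.1: the 24-month event-free proportion "is assumed to be approximately 92%, with a range of 86% to 94" per cent. SAP 4.3.2 ties the endpoints together: "Responders are subjects who show one or more new infarction(s) on MRI since screening or experience a confirmed recurrent event".

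**The concern.** When the control proportion is high by chance, its variance estimate is high too, and dividing by the small control sample makes that term dominate the denominator. So z shrinks in the direction that would favour the device. The printed test then rejects less often than its nominal level allows, on one of only two confirmatory tests, for an endpoint that by SAP 2.7.1 played no part in sizing the trial.

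An exact unconditional test keeps its size at or below 0.025 and recovers some of that loss without a single extra patient. The loss would grow if event rates ran low. SAP 4.2.2 hints at this when it says of the half-of-events point: "This milestone event had not occurred as of the completion of full enrollment in February 2015". It could also grow if missing MRI cut the evaluable numbers.

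**Working it through.** **Inputs.** n_C = 221 and n_T = 443 (Protocol 3.3; 664 × 1/3 = 221.3 and 664 × 2/3 = 442.7). Common null rates of 6–14% are 100% minus the 94–86% event-free range in SAP 2.7.1. They are borrowed from Endpoint 1. Endpoint 2 also counts silent lesions, so its rate may be higher. For power, the 55% hazard reduction of SAP 2.7.1 is borrowed as p_T = 1 − (1 − p_C)^0.45.

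**The plan's own figure.** If z were exactly standard Normal, the cut-off 1.960 would give 0.025. No Endpoint 2 power figure is readable, so none can be reproduced.

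**The mechanism in one table.** Take 25/221 control and 29/443 test events, so p_C = 0.1131, p_T = 0.0655 and the difference is 0.0477.
- Unpooled variance: 0.1131 × 0.8869/221 + 0.0655 × 0.9345/443 = 0.000454 + 0.000138 = 0.000592. The root is 0.02433 and z = 1.959, just short of rejection. The control arm supplies about 77% of the variance (0.000454/0.000592).
- Pooled rate: 54/664 = 0.0813. Variance: 0.0813 × 0.9187 × (1/221 + 1/443) = 0.000507. The root is 0.02251 and z = 2.117.

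**Exact size.** Sum the two binomial probabilities over every table with z ≥ 1.96. For Boschloo, reject when the one-sided Fisher p is at or below 0.0297, the largest cut-off whose maximum size over all common rates stays within 0.025.

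| Common rate | Unpooled z (plan) | Boschloo | Pooled z |
|---|---|---|---|
| 6% | 0.0180 | 0.0212 | 0.0289 |
| 8% | 0.0185 | 0.0216 | 0.0274 |
| 10% | 0.0199 | 0.0219 | 0.0273 |
| 12% | 0.0206 | 0.0223 | 0.0275 |
| 14% | 0.0208 | 0.0227 | 0.0270 |

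The shortfall against 0.025 is 0.0070 at 6% and 0.0042 at 14%. Boschloo recovers 0.0032 at 6% and 0.0019 at 14%. The plan's largest size over common rates of 2–30% is 0.0234. At 332/332 the same formula has size 0.0254–0.0261 for rates of 6–14%, so the conservatism comes from the 2:1 split. The plain pooled z is not a remedy, because it exceeds 0.025 throughout.

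**Power, 55% reduction, unadjusted 0.025** (gains taken before rounding).

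| Control rate | Plan | Boschloo | Gain (points) |
|---|---|---|---|
| 6% | 43.6% | 46.5% | 2.9 |
| 8% | 57.5% | 60.2% | 2.7 |
| 10% | 68.3% | 70.6% | 2.2 |
| 12% | 76.6% | 78.5% | 1.9 |
| 14% | 83.3% | 84.6% | 1.3 |
| 20% | 94.5% | 94.8% | 0.3 |

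With 90% evaluable (199/399) the gains at 6–14% are 4.4, 3.2, 2.5, 2.2 and 1.8 points. At an assumed adjusted cut-off of 0.0125 with 221/443 they are 5.3, 4.5, 3.3, 2.6 and 2.3.

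**Family-wise error.** The readable multiplicity text, at the end of SAP 4.4, describes adjusted p-values based on the correlation between the two endpoints. The simulation used 240,000 null trials for each of four assumed rate sets, endpoint correlation 0.50–0.65 and a single-step correlation-based cut-off. Family-wise error was 0.0235–0.0247 with the planned z and 0.0252–0.0258 with Boschloo (standard error 0.0003). Boschloo stays within its own cut-off (0.0119–0.0134 against 0.0135–0.0142). The excess comes from the Endpoint 1 log-rank, whose size is 0.0151–0.0162. A second simulation gave 0.023–0.026 as planned and 0.024–0.027 after the swap, a shift of the same order.

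**The case for a change.** The best case for changing is that the gain is real and almost free. It is a short edit, needs no data and uses standard software, and there is time because the primary analysis waits for the last subject's 24-month visit. The setting may also be less kind than the headline rates suggest. At a common rate of 4% the planned size is 0.0157 against 0.0189 for Boschloo, with power of 28.1% against 31.8%. Missing MRI and a stricter multiplicity cut-off can each push the gain to 4 or 5 points at the lowest rates. A Bonferroni split at 0.0125 would keep family-wise error at 0.0223–0.0239 even with Boschloo.

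The arithmetic stands, and so does the statement that the planned test is conservative at these rates. The step from there to a needed change does not:
- The larger gains depend on low rates, an unseen cut-off or missing data that the public text does not quantify. Endpoint 2 adds silent lesions to clinical events, which points toward higher rates, where the gain nearly vanishes.
- Bonferroni is not what the readable text describes. Under the method it does describe, part of the extra power is bought with slack that now offsets the log-rank, so the two options are not compared at equal family-wise error.
- The z and the reported interval for the difference share a Wald form. An exact p-value would not pair with that interval so directly, nor with an adjustment built on two test statistics and their correlation.
- Enrollment was complete in February 2015, and Protocol 2.9 describes an interim look, without hypothesis testing, that "is anticipated to occur around April 2016". Moving a confirmatory test toward more rejections at that stage would have to be documented as made without by-arm results.

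**Conclusion.** No change is called for. The planned test is standard, completely specified and consistent between the two documents. At 221/443 its one-sided size is 0.0180–0.0208 for common rates of 6–14% and at most 0.0234 for rates of 2–30%, so it errs toward caution and a positive result stands. Boschloo's test would return about 0.002–0.003 of alpha and 1.3–2.9 points of power at control rates of 6–14%, and 0.3 points at 20%. Against that stand a rise of roughly 0.001 in simulated family-wise error, to slightly above 0.025 in most settings examined, a looser link between p-value and interval, and a late change to a confirmatory test. That is a fair trade-off, and the sponsor may reasonably keep what it has.

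The size of the effect rests on rates and a hazard reduction borrowed from Endpoint 1, on near-complete MRI, and on an assumed form of the multiplicity adjustment. The unreadable power section for this test may show ample power. None of these uncertainties would make the planned test invalid at the rates considered.

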#### 4.4 Secondary Endpoints

The secondary endpoint analysis will be performed in conjunction with the primary endpoint analysis. Statistical methods for testing multiple endpoints will be utilized in the comparison of secondary endpoints across test and control to preserve the overall Type I error rate.

CONFIDENTIAL INFORMATION

MD133254 Statistical Analysis Plan Template

Revision# 1

Doc Type: GC

Based on the final analysis of correlation between the two endpoints and the unadjusted p-values obtained from the two test statistics, the appropriate adjusted p-values will be compared to the overall 1-sided  $\alpha = 0.025$  for the experiment.

## 4.6 Adverse Events

All site-reported AEs will be MedDRA coded and grouped by MedDRA System/Organ Class (SOC) and by MedDRA Preferred Term within SOC. AEs will also be grouped by seriousness (SAE vs. nonserious AE), primary relationship (device, procedure, antiplatelet medication, unrelated, and unknown) and timing of onset (procedure, pre- and postdischarge). AEs will be summarized as rates given by subject-based binomial proportions. The numerator will be the count of subjects who experienced one or more episodes of the AE of interest in the time period of interest. The denominator will be the count of subjects free of the AE of interest through the time period of interest and with sufficient clinical follow-up for the time period of interest, plus the count of subjects in the numerator. Unless otherwise specified for a particular endpoint measure, all enrolled subjects in the analysis set of interest will be considered evaluable and will contribute to the denominator.

#### 4.7 Comparison of Baseline Data

Subject demographics, clinical history, risk factors, and screening PFO characteristics will be summarized for all subjects using descriptive statistics for continuous variables (mean, standard deviation, number of observations, minimum and maximum) and discrete variables (percentage and count/sample). These measures will be compared between the test group and the control group using test methods appropriate for the measures, for example, two-sample t- or Wilcoxon rank-sum tests for continuous measures and chi-square or Fisher's exact tests for discrete measures.

#### 4.8 Subgroup Analysis of Primary Endpoints

In addition to the overall analysis, the two co-primary endpoints will also each be analyzed controlling for region, defined as enrolled at a site within the United States (US) or enrolled at a site outside of the United States (OUS).

#### 4.9 Poolability of Investigative Sites

The data from all investigative sites will be pooled based on the assumption of clinical comparability: the sites used a common protocol; the sponsor adequately monitored the study to assure protocol compliance; and the data gathering and validation mechanisms were the same across all study sites.

Analyses to justify pooling will include the following:

- The primary endpoint will be presented by site: Kaplan-Meier estimates of freedom from recurrent event will be presented for the two treatment groups.
- An assessment of the poolability of the sites using a Cox regression model of recurrent event outcome with coefficient terms for treatment group (test, control), site, and treatment group-by-site interaction. Statistical significance of the interaction term will be used to make inferences on site homogeneity. Sites with fewer than five subjects will be combined based on geographic region (US versus OUS).
- If the sites are found to be significantly heterogeneous with respect to the primary endpoint, additional analyses will be conducted to assess differences between sites in baseline and procedural variables that might explain differences in primary outcome.

Similar analyses to justify pooling for the brain infarct endpoint will be performed using a logistic regression model.

#### 4.10 Additional Analyses

Additional subgroup analyses may be performed based on variables identified to be significant predictors ( $p$ -value  $< 0.05$ ) in multivariate analyses.

Sensitivity analyses of the recurrent event and brain infarct co-primary endpoints will be conducted and will include, at a minimum, a “worst-case” analysis (subjects who withdraw or are lost to follow-up considered recurrent events in the test group and censored in the control group), a “best-case” analysis (subjects who withdraw or are lost to follow-up considered censored in the test group and recurrent events in the control group), and, if necessary, a tipping point analysis (threshold of successes vs. failures between the treatment groups at which the primary test conclusion changes).

##### 4.10.1 Evaluation of Septal Occluder Device Poolability

It is expected that shortly after approximately one-third of the subjects have been enrolled, the new study device (GORE® CARDIOFORM Septal Occluder) will become available and will be used as the device of choice within the test arm of the study. As a regulatory requirement, an assessment of poolability will be conducted for the two study device subgroups in the test arm. The statistical plan for this assessment will consist of two stages: baseline homogeneity and primary outcome comparability.

CONFIDENTIAL INFORMATION

MD133254 Statistical Analysis Plan Template

Revision#: 1

Doc Type: GC

15 of 17

For baseline homogeneity, the two test device subgroups will be compared on the following six baseline demographic and predictor covariates: age, gender, qualifying cerebrovascular event, balloon-sized PFO diameter, PFO tunnel length, and presence of atrial septal aneurysm. These subgroup comparisons will use the two-sample t-test, chi-square test, or Fisher's Exact test, depending on the distribution of the covariate.

For primary outcome comparability, covariate-by-device interactions will be assessed using Cox proportional hazards regression models where main effects for device and the covariate and the covariate-by-device interaction term will be regressed on the 24-month freedom from recurrent stroke or imaging-confirmed TIA primary endpoint; this will be performed individually for each of the six baseline covariates. Statistically significant interactions will be assessed graphically for the nature of the interaction (quantitative vs. qualitative). Qualitative interactions (difference in direction of device effect across levels of covariate) will suggest differences between the device subgroups, leading to analyses performed separately for each device subgroup. A similar approach will be used for brain infarct comparability, but using a logistic regression model for this binary endpoint.

Finally, device subgroup and any baseline covariates deemed to be different between device subgroups will be included as main effects in a Cox regression model on the primary endpoint. If the device subgroup term is statistically significant and the observed hazard reduction (test vs. control) for either of the device subgroups is less than the hypothesized 55%, then the device subgroups will not be considered outcome comparable, leading to analyses performed separately for each device subgroup. Again, a similar approach will be used for the binary brain infarct endpoint, but using a logistic regression model instead of a Cox regression model.

A significance level of  $\alpha=0.15$  will be used for these poolability tests, without correction for multiplicity. Since this evaluation plan calls for a minimum of 13 significance tests per endpoint, the overall Type-I error rate per endpoint for these analyses may exceed  $1 - (1 - 0.15)^{13} = 0.88$ .

#### 4.11 *Interim Analyses*

No interim analyses involving formal statistical testing of the study hypotheses are planned.

### 5.0 Analysis Specifications

#### 5.1 *SAS Analysis Dataset Specifications*

A specifications document is created for each analysis data set and contains, at a minimum:

- Dataset name
- Variable name
- Format
- Label
- Study database input field(s) and/or calculation logic

#### 5.2 *Statistical Output Specifications*

A specifications document is created for each statistical output (Table, Listing, or Figure) and contains, at a minimum:

CONFIDENTIAL INFORMATION

MD133254 Statistical Analysis Plan Template

Revision#: 1

Doc Type: GC

- Title and footnote information
- Column headers
- General appearance of each cell (for tables and listings)
- If the output includes a figure, either an example figure or a detailed description of the figure is included in this section
- Variables, procedures, and/or calculation logic used in the statistical output
- Change log section

### 5.3 *Verification Level for Statistical Output*

Verification levels for statistical output are defined per MD111325. The minimum required verification levels for statistical output in this study are as follows:

- All Analysis Datasets – Level 1
- All Tables – Level 1
- All Figures – Level 2
- All Listings – Level 2
- *Ad Hoc* or *Post Hoc* analyses – Level 3

## 7.0 Revision History

### Log of Changes Made to the Statistical Analysis Plan

Version Date	Initiated By	Summary of Change
15-JAN-2016	[name]	Initial Version (Revision #1)

CONFIDENTIAL INFORMATION

MD133254 Statistical Analysis Plan Template

Revision# 1

Doc Type: GC
